3.8.2 Pediatric Balance Scale (PBS)

What it assesses:

Functional balance — the child's ability to maintain equilibrium during various static and dynamic tasks in sitting and standing positions.

How it will be assessed:

The PBS consists of 14 tasks such as sitting to standing, turning, reaching, and standing with eyes closed. Each item is scored on a 5-point scale (0 to 4), with a total score out of 56. This tool has demonstrated strong reliability and validity in children with cerebral palsy and will be administered pre- and post-intervention.

3.8.3 Goniometric Measurement of Ankle Range of Motion (ROM)

What it assesses:

Passive dorsiflexion of the ankle joint – to determine changes in muscle length, joint flexibility, and soft tissue extensibility after intervention.

How it will be assessed:

A standard universal goniometer will be used to measure passive ankle dorsiflexion:

With the knee flexed (isolating the soleus)

With the knee extended (measuring the gastrocnemius-soleus complex)

Measurements will be taken in degrees and documented pre- and post-intervention.

3.9 Pilot Study:

Prior to the commencement of the main trial, a pilot study will be conducted at the same setting (The Jerusalem Princess Basma Centre at Al-Ahli Al-Arabi Hospital). The aim of the pilot is to assess the feasibility and practicality of the intervention protocol, data collection tools, and logistical arrangements. A small number of participants (e.g., 5–8 children) who meet the inclusion criteria will be involved. This pilot phase will help identify any challenges related to participant recruitment, administration of Myofascial Release (MFR), timing of assessments, or issues with outcome measurement tools such as GMFM-88 and goniometric ROM assessment.

Findings from the pilot study will be used to refine the intervention schedule, improve data collection processes, and ensure clarity and reliability of the instruments. The data

collected during the pilot will not be included in the final statistical analysis of the main study.

3.10 Validity and Reliability

This study will utilize three validated assessment tools: the Gross Motor Function Measure (GMFM-88), Pediatric Balance Scale (PBS), and Goniometry for ankle Range of Motion (ROM). All instruments are well-established in pediatric rehabilitation and have demonstrated strong validity and reliability in children with cerebral palsy.

3.10.1 Gross Motor Function Measure (GMFM-88)

Validity:

The GMFM-88 has demonstrated high content and construct validity for assessing gross motor function in children with cerebral palsy (2024).

Reliability:

The tool shows excellent test-retest and inter-rater reliability, with Intraclass Correlation Coefficients (ICCs) exceeding 0.95, confirming its consistency across different evaluators and over time.

3.10.2 Pediatric Balance Scale (PBS)

Validity:

PBS is adapted from the Berg Balance Scale and has shown strong concurrent validity with other motor performance measures in pediatric populations.

Reliability:

The scale exhibits high inter-rater and intra-rater reliability in children with CP, with reported ICCs ranging from 0.92 to 0.98 (Franjoine et al., 2003).

3.10.3 Goniometer for Range of Motion (ROM)

Validity:

Goniometry is a widely used method with established face and criterion validity when performed by trained professionals.

Reliability:

Goniometric assessments of the ankle have shown high intra-rater and inter-rater reliability, with ICCs ranging from 0.86 to 0.98, making it a dependable tool for clinical and research use (Menadue et al., 2006).

3.11 Statistical Management and Procedures

Data will be analyzed using the Statistical Package for Social Sciences (SPSS) version 22. Descriptive statistics will summarize demographic and clinical characteristics. Inferential statistics, such as paired t-tests or Wilcoxon signed-rank tests, will compare pre- and post-intervention scores within groups. Independent t-tests or Mann-Whitney U tests will compare changes between groups. A significance level of $p < 0.05$ will be set for all analyses.

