1.5 Research questions

1. Does conventional physiotherapy alone improve gross motor function, balance, and ankle range of motion (ROM) in children with cerebral palsy following Achilles tendon lengthening surgery?
2. Does the addition of Myofascial Release (MFR) to conventional physiotherapy result in greater improvement in gross motor function compared to conventional physiotherapy alone?
3. Does the addition of Myofascial Release (MFR) to conventional physiotherapy result in greater improvement in balance compared to conventional physiotherapy alone?
4. Does the addition of Myofascial Release (MFR) to conventional physiotherapy result in greater improvement in ankle range of motion (ROM) compared to conventional physiotherapy alone?

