3.1 Study design

A single-blind randomized controlled trial (RCT) will be conducted to evaluate the effect of adding Myofascial Release (MFR) to conventional physiotherapy on functional outcomes in children with cerebral palsy after Achilles tendon surgery. Participants will be randomly assigned to either an intervention group (MFR + physiotherapy) or a control group (physiotherapy only). Assessments will be conducted at baseline and after 8 weeks of intervention.

Flow Diagram

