3.4 Eligibility Criteria

Inclusion Criteria:

1. Children aged 2 to 5 years.
2. Diagnosed with spastic cerebral palsy (GMFCS levels I–IV).
3. Have undergone Achilles tendon lengthening surgery within the past 3 months.
4. Medically stable and cleared to begin physiotherapy.
5. Parental/guardian consent to participate in the study.

Exclusion Criteria:

1. Diagnosis of other neuromuscular or developmental disorders.
2. Received Myofascial Release therapy in the past 6 months.

3. Severe cognitive or behavioral impairments that interfere with following instructions.
4. Participation in another rehabilitation study in the past 3 months.

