3.5 Sample Size and Sampling Process

A sample size of 40 participants (20 per group) will be targeted, based on feasibility, resource availability, and statistical power considerations. A consecutive sampling method will be employed, selecting eligible participants who consent to participate during the recruitment period.

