3.6.2 Timing of Data Collection

Data will be collected at the following time points:

Pre-Intervention (Baseline):

Before to the start of any physiotherapy sessions, baseline data will be recorded to establish initial levels of function and range of motion.

Post-Intervention (After 8 weeks):

After the completion of the intervention period, a post-treatment assessment will be conducted to measure changes in gross motor function and ankle dorsiflexion ROM.

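### Section 3.11 compares changes without baseline adjustment: a valid test, but ANCOVA on each outcome's own baseline may be more precise than the t-test at a small, bounded cost

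*Combined protocol and SAP*

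**What the plan says.** Section 3.11 (Statistical Management and Procedures) gives one between-group analysis: "Independent t-tests or Mann-Whitney U tests will compare changes between groups". The paired tests in the same section look within each arm and do not estimate a treatment difference. No ANCOVA or other baseline-adjusted model appears anywhere in the document.

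Every outcome nevertheless has its own baseline:
- Section 3.1: "Assessments will be conducted at baseline and after 8 weeks of intervention".
- Section 3.6.2, before treatment: "baseline data will be recorded to establish initial levels of function and range of motion".
- Section 3.8.2, on the Pediatric Balance Scale (PBS): it "will be administered pre- and post-intervention".
- Section 3.8.3, on dorsiflexion with the knee flexed and extended: "Measurements will be taken in degrees and documented pre- and post-intervention".

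On size, section 3.5 states: "A sample size of 40 participants (20 per group) will be targeted".

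**The concern.** Research questions 2 to 4 in section 1.5 all rest on this one comparison. The second, for instance, asks whether adding myofascial release will "result in greater improvement in gross motor function compared to conventional physiotherapy alone".

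A t-test on changes subtracts the whole baseline score, which fixes the slope of outcome on baseline at 1. ANCOVA estimates that slope. When the true slope is below 1, the change score over-corrects, and any chance baseline difference between arms adds noise to the estimated effect.

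With 20 per arm, all analysed, and a two-sided 5% level (the plan does not state sidedness), the t-test reaches 80% power only for a difference of about 0.91 SD of change. Precision obtainable from data already being collected is therefore worth considering.

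**Working it through.** **Inputs.** N = 40, 20 per arm (section 3.5). Significance level 0.05 (section 3.11), taken as two-sided. One baseline and one 8-week value per outcome (section 3.1). The correlation r is not in the documents; the assumed range is 0.5 to 0.95. The ratio k of 8-week SD to baseline SD is not given either; k = 1 unless stated. The plan attaches no effect size, SD or power to its 40 participants, so there is no figure of its own to reproduce.

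**Variances with equal SDs** (σ common, n per arm, baseline normally distributed):
- Change-score difference: 2σ²(1−r) × 2/n.
- ANCOVA difference: σ²(1−r²) × 2/n × (N−3)/(N−4). The last factor is the cost of estimating the slope, 37/36 = 1.0278 at N = 40.
- Ratio, ANCOVA to change score: (1+r)/2 × 37/36.

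The last column below is 20 divided by the ratio: the number per arm at which change scores would match ANCOVA with 20.

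| r | Ratio | Saving | ANCOVA power where the t-test has 80% | Equivalent per arm |
|---|---|---|---|---|
| 0.5 | 0.771 | 22.9% | 89% | 25.9 |
| 0.7 | 0.874 | 12.6% | 85% | 22.9 |
| 0.8 | 0.925 | 7.5% | 83% | 21.6 |
| 0.9 | 0.976 | 2.4% | 81% | 20.5 |
| 0.95 | 1.002 | −0.2% | 80% | 20.0 |

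Break-even is r = 2 × 36/37 − 1 = 0.946. A simulation of 200,000 trials gave ratios of 0.770 at r = 0.5 and 1.002 at r = 0.95. The type I error of the change-score t-test was 0.049 to 0.050.

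**Unequal SDs.** The ratio becomes k²(1−r²)/(1+k²−2rk) × 37/36. At r = 0.5, 0.7, 0.8, 0.9 and 0.95:
- k = 1.2: 0.895, 0.993, 1.025, 1.004, 0.902.
- k = 0.8: 0.587, 0.645, 0.658, 0.625, 0.534.

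So the near-zero saving at r = 0.95 is particular to equal SDs. It becomes about 10% at k = 1.2 and 47% at k = 0.8.

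**Largest possible loss.** The denominator minus the numerator of the first factor is 1+k²−2rk − k²(1−r²) = (1−rk)², which is never negative. That factor therefore never exceeds 1, and the ratio never exceeds (N−3)/(N−4) for any r or k. The loss is at most 37/36 − 1 = 2.8% with 40 analysed and 29/28 − 1 = 3.6% with 32. Counting the lost degree of freedom (37 instead of 38), it is about 3.0% in squared interval width at N = 40.

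**Chance imbalance.** With equal SDs, a baseline difference D moves the change-score estimate by −(1−r)D. The probability of a difference of at least 0.4 SD is 2 × (1 − Φ(0.4/√(2/20))) = 0.206. At 0.4 SD the shift is 0.20 baseline SD at r = 0.5 and 0.04 at r = 0.9. This is already in the table: apart from the slope-estimation factor, 2(1−r) = (1−r²) + (1−r)², and the last term is the variance of that shift. At r = 0.5 this reads 1.00 = 0.75 + 0.25.

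**Against Mann-Whitney on changes.** Simulated power (%), Mann-Whitney / ANCOVA, with 20 per arm, 20,000 replicates per setting, normal baseline, equal SDs and an effect of 0.909 SD of change:

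| Error shape | r = 0.5 | r = 0.7 | r = 0.9 | r = 0.95 |
|---|---|---|---|---|
| Normal | 77.8 / 89.1 | 77.8 / 84.8 | 77.9 / 81.0 | 77.9 / 80.1 |
| t, 3 df | 89.4 / 90.2 | 91.5 / 87.6 | 94.0 / 84.6 | 94.5 / 84.5 |
| Exponential | 87.3 / 88.0 | 90.2 / 84.6 | 92.5 / 81.1 | 92.8 / 80.1 |
| Lognormal | 95.2 / 88.9 | 97.9 / 87.0 | 99.1 / 85.0 | 99.2 / 84.2 |

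With normal errors ANCOVA leads by about 2 to 11 points. With the other shapes it trails by about 4 to 15 points at r of 0.7 or more, and by about 6 points at r = 0.5 with lognormal errors.

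**The case against.** The strongest reply is that nothing here is wrong. The research questions ask about greater improvement, the plan compares improvement, and the test is unbiased over randomisations. That stands. A reader might infer that the unadjusted test is invalid, or that chance imbalance biases it as a further harm. Neither follows: the simulated error rate is nominal, and the imbalance shift averages to zero and is the mechanism of the variance loss already counted.

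A second reply is that r is probably high. Section 3.4 admits GMFCS I to IV, and sections 3.10.1 and 3.10.2 quote ICCs above 0.95 for GMFM-88 and of 0.92 to 0.98 for PBS. These are reliabilities, not 8-week correlations, but they make a high r plausible for those two outcomes. The equal-SD saving would then be about 2% or less. Recent surgery could lower r; the documents do not say by how much. So 23% cannot be read as the expected gain.

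A third reply is that Mann-Whitney is also in the plan and can beat ANCOVA. That stands too, so the change should not be called free. The simulations also use normal baselines and unbounded scores, whereas PBS runs from 0 to 56 with mostly standing tasks, and floor effects are plausible. An illustrative check with assumed PBS means by GMFCS level (44, 34, 12 and 0), clipped to the scale, gave r of about 0.98 and a variance ratio of about 1.03. With skewed gains, power was 0.79 for the t-test, 0.82 for Mann-Whitney and 0.78 for ANCOVA. A gain is not assured.

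Finally, the open choice between two tests in section 3.11 is a separate matter. Naming either planned test would settle it, so it adds no weight here.

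**Conclusion.** The point holds as a cheap improvement of low severity, not as an error in the plan. Against the change-score t-test, own-baseline ANCOVA saves between about 23% and nothing as r goes from 0.5 to 0.95 with equal SDs. It loses at most 2.8% if all 40 are analysed. The formula is secure given a linear model with a normally distributed baseline; the benefit in this trial is uncertain, because r and the SD ratio are assumptions. It is likely to be small for GMFM-88 and PBS. The documents offer no 8-week correlation for dorsiflexion, where a larger gain remains possible. The advantage does not extend to Mann-Whitney on changes when errors are clearly non-normal.

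**What to change.** In section 3.11, replace the between-group sentence with:

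> For each outcome the between-group analysis is the arm coefficient from an ANCOVA of the 8-week score on arm and the baseline score of the same outcome, reported as an adjusted mean difference with 95% CI. A Mann-Whitney U test on changes is a prespecified sensitivity analysis.

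Fix this before outcome data are seen, and do not switch between the two on the strength of residual checks. ANCOVA should replace the open choice, not become a third option.

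The cost is two sentences, with no new measurements and no change in conduct. The statistical price is one degree of freedom, at most about 3% in variance against the t-test with 40 analysed, and the loss of power against Mann-Whitney shown above if errors are markedly skewed or heavy-tailed. Keeping Mann-Whitney as a sensitivity analysis makes that case visible.

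This wording does not settle how several outcomes are handled together, or which ankle is analysed when both were operated on. The plan needs to state both separately.

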3.6.3 Data Collectors

Trained physiotherapists who are not involved in the intervention sessions will perform all assessments to avoid bias. They will undergo calibration and training sessions to standardise the assessment procedures and ensure inter-rater reliability.

3.7 Intervention:

This study will include two intervention arms:

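### The between-group comparison of change is valid but unadjusted: with GMFCS I–IV eligible and 20 children per arm, adjusting for GMFCS level and baseline score is a cheap gain in precision

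*Combined protocol and SAP*

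**What the plan says.** - **Analysis (3.11).** "Independent t-tests or Mann-Whitney U tests will compare changes between groups". No covariate or stratum is named, and clinical characteristics are only described.
- **Eligibility (3.4).** "Diagnosed with spastic cerebral palsy (GMFCS levels I–IV"). GMFCS is not used anywhere else in the plan.
- **Size (3.5).** "A sample size of 40 participants (20 per group) will be targeted". No effect size, SD, power or dropout rate is given.
- **Allocation (3.1).** "Participants will be randomly assigned to either an intervention group (MFR + physiotherapy) or a control group (physiotherapy only"). The visible text gives no stratification, sequence method or concealment method. The flow diagram is not shown.
- **Blinding and assessment (3.1, 3.6.3).** "A single-blind randomized controlled trial (RCT) will be conducted", without naming the blinded party. "Trained physiotherapists who are not involved in the intervention sessions will perform all assessments to avoid bias".
- **Baseline (3.6.2).** "Before to the start of any physiotherapy sessions, baseline data will be recorded". The anchor is the first treatment session, not assignment.
- **Balance scale (3.8.2).** "Each item is scored on a 5-point scale (0 to 4), with a total score out of 56".

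**The concern.** Four severity levels in a 40-child trial could make change scores vary for reasons unrelated to myofascial release (MFR). On the Pediatric Balance Scale (PBS) there is a plausible mechanism. Items 4 and 6 to 14 in the appendix form are done standing, which is 10 of 14 items and 10 × 4 = 40 of 56 points. A child who cannot stand unsupported has little room to change on them. If gain depends on severity, an unadjusted comparison has a wider interval, and an unlucky split moves the estimate because of case mix.

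The second, smaller matter is baseline timing. Every between-group test uses change, so the baseline score enters each endpoint directly. The GMFM-88 and PBS are scored by an observer, and the goniometer is read by hand. A baseline scored with the arm known could bias the change score, and no later analysis would remove that.

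**Working it through.** **Inputs from the documents:** 20 per arm (3.5); significance level 0.05 (3.11), taken as two-sided because sidedness is not stated; GMFCS I–IV (3.4).

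**Assumptions, not in the documents:** K = 16 of 40 children at levels III–IV (range 10 to 20); within-level SD of change = 1; levels III–IV gain g SD less, with g = 0, 0.5 or 1; the same treatment effect at every level.

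**1. The plan's own figure.** The sample size of 40 cannot be reproduced, because no effect, SD or power is stated. Working backwards with the noncentral t distribution, 20 per arm gives 80% power for 0.909 SD. That effect is used below.

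**2. Chance imbalance.** The number of III–IV children in one arm is hypergeometric (40, K, 20). The probability that the arms differ by 4 or more such children is 27% for K = 10, 33% for K = 16 and 34% for K = 20. At K = 16 that is about 17% in each direction.

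**3. Loss of precision, by formula.** Ignoring level adds p(1−p)g² to the variance of change. With p = 16/40 = 0.4 this is 0.24g².
- g = 0: variance 1.00, effect 0.909, power 80%.
- g = 0.5: variance 1.06, effect 0.909/√1.06 = 0.883, power 77.7%.
- g = 1: variance 1.24, effect 0.909/√1.24 = 0.816, power 71.1%.

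**4. Simulation (60,000 trials per row, K = 16), t-test against change adjusted for GMFCS group:**

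| Gap g | Power, unadjusted | Power, adjusted | Mean 95% CI width (SD) | 40 adjusted children are worth |
|---|---|---|---|---|
| 0 | 80.0% | 78.8% | 1.27 vs 1.29 | 39 unadjusted |
| 0.5 SD | 77.4% | 78.6% | 1.31 vs 1.29 | 41 |
| 1 SD | 70.8% | 78.9% | 1.42 vs 1.29 | 48 |

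The last column is 40 × (ratio of the SDs of the estimate)². For g = 1 it is 40 × (0.3535/0.3210)² = 48.5. At g = 1, power is 73% vs 79% for K = 10, and 71% (70.5%) vs 79% for K = 20.

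**5. Within the imbalanced splits, at g = 1 only.** A difference of exactly 4 children shifts the unadjusted estimate by 4/20 × 1 = 0.20 SD. Averaged over differences of 4 or more, the shift is about 0.24 SD. With the extra III–IV children in the MFR arm, power is 46% unadjusted vs 78% adjusted. In the mirror case it is 91% vs 77%. With no true effect, false positives in these splits are 8% vs 5%. Over all splits both methods hold 5%.

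**6. Adding the baseline score.** For pre–post correlation r, the variance of ANCOVA relative to change scores is (1+r)/2. For r = 0.9 this is 0.95, and 40/0.95 = 42 children. For r = 0.5 it is 0.75, and 40/0.75 = 53 children. After the cost of estimating the coefficient, the range is about 41 to 52. The values of r are assumed.

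**7. Worst-case cost of two covariates.** If neither GMFCS nor baseline explains any variation in change, simulated power falls from 80.0% to 77.6%.

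**8. Baseline timing.** No arithmetic applies. Section 3.6.2 places baseline before treatment, 3.6.3 uses assessors who do not treat, and 3.1 calls the trial single-blind. None of the three places baseline before assignment, says how assignment is concealed, or says that the assessors are the masked party.

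**The case against.** **The planned analysis is conventional and contains no error.** This stands. Adjustment improves efficiency and does not rescue an invalid test. A reader might infer from the 8% figure that the trial's false-positive rate is inflated. It is not: that figure conditions on the worst third of splits and on a 1 SD gap.

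**The benefit rests on an undocumented gap.** This also stands. At 0.5 SD adjustment is worth about one child, and at zero it costs one. Only near 1 SD is the gain material, and no document supports that value.

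**The mechanism covers one outcome.** The floor argument concerns the PBS. It gives no reason for passive ankle dorsiflexion, and little for the GMFM-88 total, where lying, sitting and crawling/kneeling are three of five equally weighted dimensions. The documents also do not say which GMFCS levels cannot stand, so the I–II vs III–IV cut is a judgement.

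**Children at a floor would not show the full treatment effect.** That is fair. At a 1 SD gap, if III–IV children have half the effect, power is 47–48% unadjusted vs 59% adjusted; if they have none, it is 27% vs 37%. Adjustment still helps, but 71% vs 79% does not describe that case.

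**Mann-Whitney suits a bounded ordinal score.** This is why it should stay as a sensitivity analysis.

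**The baseline point is silence, not contradiction.** A reader might infer that baseline will be scored with the arm known, or that assessors are unmasked. The documents do not support this. Baseline precedes all physiotherapy, assessors do not treat, masking is implied, and the flow diagram that might show the order is not visible.

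**Conclusion.** The point holds as a recommended improvement with medium confidence. The unadjusted tests in 3.11 are valid, but they forgo precision and leave chance GMFCS imbalance uncorrected in a trial of 20 per arm. With 16 of 40 children at levels III–IV and an effect of 0.909 SD, both assumed, adjusting for GMFCS alone is worth between −1 and +8 points of power for gaps of 0 to 1 SD. Adding the baseline score may be worth as much again, depending on the pre–post correlation. The PBS is the only outcome for which the documents themselves suggest why severity should matter.

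Baseline order, concealment and masking form a secondary safeguard. The text does not rule out scoring baseline after the arm is known, but it does not show that this will happen, and no bias has been demonstrated.

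**What to change.** **Section 3.11**, replace the between-group sentence with:

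> For each outcome, the primary between-group analysis is ANCOVA of the 8-week score on arm, baseline score and GMFCS level (I–II vs III–IV, recorded at screening), reporting the adjusted difference with its 95% CI. The Mann-Whitney test of change is a sensitivity analysis.

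This also settles which test is primary, which the current text leaves open.

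**Sections 3.1 and 3.6.2**, add:

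> The baseline assessment is completed before the child's concealed allocation is opened.

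**Section 3.6.3**, add as a clarification:

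> These assessors are masked to allocation.

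Stratified randomisation is optional, since the model handles the imbalance.

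**Cost.** Two degrees of freedom per outcome, about two points of power at worst (80% to 78%). Each child's GMFCS level must be written down; the plan does not say that it is recorded, but screening already has to determine it. A simple means of concealment is needed, such as sealed envelopes held by someone who does not enrol, treat or assess. No extra visits or measurements are required, and SPSS fits the model. If enrolment has begun, fix the model before any between-arm data are examined.

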1.4 Objectives of the Study

1.4.1 General Objective:

To evaluate the effectiveness of adding Myofascial Release (MFR) to conventional physiotherapy on functional outcomes and balance in children with cerebral palsy following Achilles tendon lengthening surgery in the Gaza Strip.

1.4.2 Specific Objectives:

1. To evaluate the effectiveness of conventional physiotherapy on functional outcomes in children with cerebral palsy following Achilles tendon lengthening surgery in the Gaza Strip.
2. To evaluate the effectiveness of conventional physiotherapy on balance in children with cerebral palsy following Achilles tendon lengthening surgery
3. To evaluate the effectiveness of adding Myofascial Release (MFR) to conventional physiotherapy on functional outcomes and balance in children with cerebral palsy following Achilles tendon lengthening surgery.

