2.1.2 Dependent Variables

Gross Motor Function

This refers to a child's ability to perform large muscle activities, such as sitting, standing, and walking. It will be measured using the Gross Motor Function Measure (GMFM), a validated scale for children with CP.

[figure not shown]
Range of Motion (ROM)

Specifically focused on ankle dorsiflexion and plantarflexion, ROM will be measured using a goniometer to assess joint mobility post-surgery and throughout rehabilitation. Improved ROM is essential for better gait and balance.

Balance:

The ability to maintain upright posture and stability during static and dynamic tasks. It will be measured using the Pediatric Balance Scale (PBS), a validated tool for young children with CP.

In this study, the independent variables—CPT and MFR—are expected to influence the dependent outcomes: gross motor function, balance, and ankle ROM. MFR is hypothesized to enhance the structural readiness of muscles and fascia, reducing tone and improving tissue mobility. This, in turn, may augment the efficacy of CPT by enabling more effective execution of strengthening, balance, and gait exercises. The synergistic combination is thus anticipated to yield greater improvements in functional outcomes compared to CPT alone.

Conceptual framework (Self developed)

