3.6.1 Assessment study Tools

The following tools will be used to collect data on the primary outcome measures:

Gross Motor Function Measure-88 (GMFM-88):

This is a standardised observational instrument designed to measure changes in gross motor function in children with cerebral palsy. It consists of 88 items categorised into five dimensions: lying and rolling, sitting, crawling and kneeling, standing, walking, running, and jumping. GMFM-88 has been validated and widely used in pediatric rehabilitation settings (Choi, 2024).

Pediatric Balance Scale (PBS):

An adapted version of the Berg Balance Scale for children, used to assess functional balance in sitting and standing tasks. It consists of 14 items scored on a 5-point scale, and has demonstrated strong validity and inter-rater reliability in children with CP.

Range of Motion (ROM):

Passive ankle dorsiflexion will be measured using a standard universal goniometer. Measurements will be taken with the knee both flexed and extended to assess the length and flexibility of the gastrocnemius-soleus complex. This will provide an objective evaluation of the effect of the interventions on joint flexibility.

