3.8.1 Gross Motor Function Measure-88 (GMFM-88)

What it assesses:

Gross Motor Function – the child's ability to perform age-appropriate motor activities such as sitting, standing, crawling, walking, and jumping.

How it will be assessed:

The GMFM-88 includes 88 items divided across five domains:

Lying and Rolling

Sitting

Crawling and Kneeling

Standing

Walking, Running, and Jumping

Each item is scored on a 4-point ordinal scale from 0 (does not initiate) to 3 (completes the task fully). The total and domain-specific scores will be calculated.

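### Three unranked primary outcomes are each tested at 0.05 with no success rule or multiplicity control, so the false-positive rate of an MFR effectiveness claim is not fixed: at most 5% under some readings, about 11-19% if any one outcome may count

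*Combined protocol and SAP*

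**What the plan says.** Section 3.6.1 introduces its three tools with "The following tools will be used to collect data on the primary outcome measures". The tools are GMFM-88, PBS and passive ankle dorsiflexion, and none is placed above the others. For dorsiflexion it adds "Measurements will be taken with the knee both flexed and extended", and section 3.8.3 repeats the two positions.

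Section 3.11 is the whole statistical plan. On the comparison of arms it says "Independent t-tests or Mann-Whitney U tests will compare changes between groups", and on error control only "A significance level of $p < 0.05$ will be set for all analyses". It also lists paired tests within each arm. It contains no hierarchy, adjustment or success rule, and no other section supplies one.

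The aims are framed in two ways. Specific objective 3 in section 1.4 is a single aim: "To evaluate the effectiveness of adding Myofascial Release (MFR) to conventional physiotherapy on functional outcomes and balance". Section 1.5 instead asks one between-group question per outcome: question 2 on gross motor function, question 3 on balance, and question 4 on whether adding MFR will "result in greater improvement in ankle range of motion (ROM) compared to conventional physiotherapy alone". The plan does not say which framing governs the conclusion.

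**The concern.** With several primary outcomes and no success rule, 0.05 is the error rate of each test. It is not necessarily the error rate of the statement that adding MFR is effective. Someone writing up the trial could take the single objective in section 1.4 as met once any one outcome reached significance, and nothing written in advance says whether that is enough. A rule chosen after the results are known could be shaped by them, so the repair is credible only if made before outcome data are analysed.

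**Working it through.** **Inputs from the plan.** 20 children per arm (section 3.5); 0.05 per test, applied to change between groups (section 3.11); one follow-up assessment at 8 weeks (sections 3.1 and 3.6.2), so time points add no multiplicity. The plan states no overall error rate, so there is no figure of its own to reproduce.

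**Assumptions.** Two-sided tests (sidedness is not stated), no true MFR effect, and a common correlation r between outcome changes. The documents give no correlation, so a range is shown.

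**Number of tests.** Three if ROM is reduced to one endpoint (GMFM-88 total, PBS total, ROM); four if each knee position is tested. PBS stays in the count: section 3.6.2 does not mention it at follow-up, but section 3.8.2 has it administered before and after the intervention.

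**Independent outcomes.** The chance of at least one p < 0.05 among k tests is 1 - 0.95^k:
- k = 2: 1 - 0.9025 = 0.0975
- k = 3: 1 - 0.8574 = 0.143
- k = 4: 1 - 0.8145 = 0.185

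Counting only results that favour MFR: 1 - 0.975^3 = 0.073 and 1 - 0.975^4 = 0.096, against 0.025 for one test.

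**Correlated outcomes.** Simulation with 20 per arm, pooled t-tests on normal changes and 100,000 replicates per cell:

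| Rule | r = 0 | r = 0.5 | r = 0.7 | r = 0.9 |
|---|---|---|---|---|
| Either of 2 (ROM, two knee positions) | 9.8% | 9.2% | 8.4% | 7.2% |
| Any of 3 | 14.1% | 12.6% | 11.1% | 8.5% |
| Any of 4 | 18.4% | 15.9% | 13.1% | 9.4% |
| Any of 3, favouring MFR | 7.2% | 6.4% | 5.6% | 4.3% |
| Any of 4, favouring MFR | 9.5% | 8.0% | 6.6% | 4.7% |

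With four tests and unequal correlations (ROM pair 0.5-0.9, GMFM-88 with PBS 0.5-0.7, cross-correlations 0.2-0.5), the any-one rate was 13.8-16.8%, inside the range above.

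**Rate under each reading.**
1. Any one outcome suffices: the any-of-3 or any-of-4 rows.
2. Each question in section 1.5 is its own conclusion: GMFM-88 total 5%, PBS 5%, ROM about 7-10% if either knee position may answer question 4.
3. All outcomes must be significant: at most 5%, because every single test must pass.

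**Check of the fix (200,000 replicates; r = 0, 0.5, 0.7).** Chance of any false claim: primary at 0.05 with gated Holm, 5.0% throughout; Holm across four, 4.9%, 4.4% and 3.8%. A primary at 0.05 with ungated Holm on the secondaries gives 9.7%, 8.6% and 7.5%, so the gate is needed.

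**Power cost (20 per arm, two-sided t-test).** The strictest Holm step is 0.05/3 = 0.0167 for three tests and 0.05/4 = 0.0125 for four. The effect detectable with 80% power is 0.91 SD at 0.05, 1.06 SD at 0.0167 and 1.10 SD at 0.0125. For a true effect of 0.91 SD, power is 80%, 64.5% and 60% respectively.

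**The case against.** The strongest reply is that section 1.5 is the most specific statement of intent and asks one question per outcome. Three separate answers, each at 5%, need no joint adjustment. Nor does objective 3 say that any one outcome is enough; requiring all of them would be conservative. This stands to the extent that the 11-19% figures are conditional and cannot be stated as the trial's error rate. It does not remove the point: the plan never chooses between the readings, and even question by question ROM has two measurements and no rule for combining them.

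Four stronger readings are tempting, and the documents do not support them.
- *A significant pre-post change in the MFR arm could pass as evidence for MFR.* Questions 2-4 define the benefit as greater improvement than physiotherapy alone, and section 3.11 assigns between-group tests to that comparison. The within-group tests have their own use, in question 1 and objectives 1-2, and are not part of this count.
- *The choice between t-test and Mann-Whitney inflates the error further.* It does so in the way feared only if the smaller p-value is taken, and section 3.11 does not say that.
- *The GMFM-88 domains add five tests.* Section 3.8.1 says "The total and domain-specific scores will be calculated"; it does not say that the domains are tested.
- *Plantarflexion is a further endpoint.* Section 2.1.2 says "Specifically focused on ankle dorsiflexion and plantarflexion, ROM will be measured using a goniometer", but sections 3.6.1 and 3.8.3 measure dorsiflexion only.

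**Conclusion.** The omission is certain: the primary outcomes are unranked, every test is at 0.05, and there is no success rule or multiplicity control. Its size is conditional. If any one outcome may count, the false-positive chance is about 11-14% (three tests) or 13-19% (four) for correlations of 0.7 to 0, and about 8-10% at 0.9, against 5%. Results favouring MFR occur at about half those rates, against 2.5%. If questions 2-4 are answered separately, the inflation is confined to ROM. If all outcomes must be significant, there is none.

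A reader might infer that the trial simply runs at an error rate of up to 19%. The plan does not say so, because it adopts no rule at all. The defect is that the rate cannot be determined from what is written. The percentages also rest on assumed correlations and normally distributed changes.

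**What to change.** Before any outcome data are analysed:

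1. In section 3.6.1, name one primary outcome, chosen by the sponsor and defined as a single variable. An example is the between-group difference in change from baseline to 8 weeks in GMFM-88 total percentage score. State which total is meant, since the appendix form prints one without and one with aids or orthoses.
2. In section 3.11, fix one two-sided between-group test for it at 0.05, for example the t-test on change with Mann-Whitney as a labelled sensitivity analysis. Base the MFR effectiveness conclusion on that test.
3. Make PBS total and dorsiflexion at each knee position secondary. Fix each test in advance and define one value per child at each knee position, because the plan does not say which ankle counts if both were operated on. Apply Holm across the three only if the primary is significant; otherwise report estimates with 95% confidence intervals.
4. Report GMFM-88 domain scores as estimates with 95% confidence intervals and no significance claim.
5. Keep the within-group tests for question 1 and objectives 1-2, and state that claims about adding MFR rest only on between-group tests.

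If the sponsor will not rank the outcomes, replace items 1-3 with Holm across the four between-group tests, each defined and fixed in advance, and claim an effect only for each outcome that is significant under Holm.

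**Cost.** The edits are to wording and need no extra data. A named primary loses no power to multiplicity. However, an isolated p < 0.05 on a secondary no longer supports a claim, and under the gate no secondary can if the primary misses. Outcomes tested under Holm bear the power loss shown in the working. A t-test fixed in advance may also lose some power if changes are strongly skewed.
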